## Preeclampsia and contact activation

### Background

Preeclampsia (PE) is from ancient time known as "a disease of theories" and the symptoms of PE have been known for several thousand years. Early descriptions of the disease are published in Kahun Medical Papyrus in 1,850 BC. Many attempts have been made to clarify the pathophysiology of PE since then and great progress has been achieved in particular during the last 20 years (1) but many questions remain to be answered. The risk factors for PE include, e.g. previous PE, familiar disposition, nulliparity, chronic hypertension, diabetes, adiposity, lupus erythematosus, and antiphospholipid syndrome (2). PE is worldwide a major contributor to maternal mortality and severe perinatal complications such as prematurity and intrauterine growth retardation (IUGR). Approximately 5% of all pregnancies are affected by PE (1), and approximately 2,500 cases of PE are registered in Denmark annually.

The pathophysiology of PE is related to both placental and maternal conditions. Incomplete remodelling of the spiral arteries in the uterus causes increased vascular resistance and hypo-perfusion of the placental tissue. The hypo-perfusion may affect the utero-placental blood flow leading to placental thrombosis (3), IUGR, affection of foetal development (2), and death (4). PE is a major risk factor for iatrogenic induced prematurity causing a variety of neonatal complications and sequelae (5). The maternal causes of PE are related to systemic inflammation, endothelial dysfunction, and hypercoagulability (2). These conditions may in complicated cases affect multiple organs such as the brain, the liver, and the kidneys. Moreover, both the mother and the baby affected by PE have increased risk for development of cardiovascular disease later in life (6).

In the guideline from the Danish Society of Obstetrics and Gynaecology (7), PE is defined as gestational hypertension accompanied by newly developed proteinuria and/or indications of organ dysfunction such as (one or more of:) thrombocytopenia, haematological complications, kidney affection, liver affection, pulmonary oedema, neurological complications, and IUGR.

It is a challenging task to treat PE. The condition is unpredictable both with respect to the development of the disease and the many symptoms. The patients may clinically demonstrate stable and paraclinical conditions, while they a few minutes later may be severely ill, and the treatment of PE often requires a major interdisciplinary collaboration. The pathogenesis for development of PE is unclear and a better understanding of the pathogenesis will undoubtedly lead to new treatment modalities with maintenance of the pregnancy as close to term without risk for mother and child as the target of the treatment.

Previous studies have demonstrated that misfolded proteins are associated with PE (8), supporting the hypothesis that the contact activation system (CAS) in blood may play a significant role in the pathogenesis of PE because misfolded proteins have the capacity to activate CAS (9, 10). Studies performed decades ago have investigated specific CAS-proteins in women with PE, but the relation between CAS, misfolded proteins, and the pathogenesis of PE has not been conceptually addressed previously.

### The contact activation system

The contact activation system of blood (CAS) is initiated by interactions between the plasma proteins coagulation factor XII (FXII) and prekallikrein (PK) and activating surfaces. FXII binds directly to the surface,

whereas the binding of PK is facilitated through the cofactor high molecular weight kininogen (HHWK). FXII and PK are both proenzymes and may upon binding undergo activation to the enzymes activated FXII (FXIIa) and kallikrein (KK). Subsequently, the activation is amplified by KK-induced feedback activation of more FXII-molecules. KK also has the capacity to cleave HMWK leading to formation of degradation products including the inflammatory peptide bradykinin. Contact activation may also result in generation of plasmin, which is the ultimate fibrinolytic enzyme, and contact activation may in presence of calcium lead to formation of thrombin, which is the key enzyme in the coagulation process (11).

Collagen, polyphosphates, and RNA are potential physiological activators of CAS (12). Several studies, however, have demonstrated that binding of FXII and PK to misfolded proteins, in particular, plays a significant role in the initiation of CAS (10, 13). The interaction between FXII and the activating surface as well as the presence of calcium determine the further progress of the reactions initiated by CAS (12). Several inhibitors regulate the activity of CAS but particularly the regulation induced by C1-esterase inhibitor (C1-inh) and alpha-2-macroglobulin (a2M) is important. Mutations in the SERPING1 gene encoding for C1-inh may modify C1-inh and induce misfolding of the protein turning the inhibitor into a potent activator of CAS (9). Misfolded C1-inh may be present in plasma in patients suffering from hereditary angioedema (HAE). In these patients, misfolded C1-inh stimulates release of bradykinin, which induces the severe and acute oedema attacks characterizing patients with HAE (14). a2M regulates the activity of CAS by entrapping FXIIa and KK. The structure of a2M is modified by this action, and the plasma concentration of the modified molecule, entitled fast-form a2M (F-a2M), reflects the contact activation that may have occurred in a given patient plasma (15). The potential of CAS can be assessed by determination of the amount of KK that can be generated after activation of CAS (16).

#### *Preeclampsia and contact activation*

Only few studies have investigated the effect of PE on the CAS proteins (17-21). Most studies are more than 30 years old, and it is not possible to reveal the complex interactions characterizing the initiation and propagation of CAS with the methods used previously. Studies have, however, shown that the plasma concentration of PK increases through pregnancy in healthy women, while PK and C1-inh decrease in women developing PE (19, 22). These findings suggest that KAS is activated in women suffering from PE.

Studies have indicated that PE shares homology with other conformational diseases (8) including among others Alzheimers disease, diabetes type 2 (23), HAE (9, 14) chronic obstructive pulmonary disease, and liver disease (24). Conformational diseases are related to misfolding of proteins regulating the class of enzymes called serine proteases including among others the enzymes involved in CAS (25). These regulating inhibitors are known as serpins. Under certain circumstances serpins may misfold and lose their inhibitory capacity resulting in abundant and uncontrolled proteolytic activity. Notably, misfolded proteins are identified in patients with PE and as they are potent activators of CAS (9, 10), these findings suggest that CAS is involved in the pathophysiology related to development of PE.

#### *Preeclampsia and plasminogen activator inhibitor type 2*

Plasminogen activator inhibitor type 2 (PAI-2) is a placenta derived serpin regulating the activity of urokinase (uPA) which is a fibrinolysis promoting protease. The plasma concentration of PAI-2 increases to high levels through pregnancy and decreases to undetectable levels immediately after delivery (26). Pregnant women with PE have lower plasma concentration of PAI-2 than healthy women (27), and reduced

concentrations of PAI-2 are observed in women with PE as early as in 16th gestational week (28). Whether this reduction in plasma PAI-2 is related to polymerisation and misfolding of PAI-2 is unknown.

PAI-2 controls the fibrinolytic activity in trophoblasts by inhibiting uPA and PAI-2 is by this action involved in the adhesive, tissue modelling and invasive processes characterizing the activity of trophoblasts which is prerequisite for the development of normal spiral arteries in the uterus (29). Disturbances in the balance between uPA and PAI-2 may compromise the development of the spiral arteries and by that contribute to the development of PE.

PAI-2 is the only serpin that polymerizes spontaneously under physiological conditions. Intracellular PAI-2, however, does not polymerize but is characterized by an active, stable and reduced form and is capable of inhibiting uPA. Extracellular PAI-2 is active but may polymerize spontaneously. The polymerization is dependent on the oxidative processes characterizing the extracellular milieu (30). At the cellular level, PE is characterized by release of free radicals from placenta (31). The induced increased oxidative stress may potentially cause uncontrolled polymerization and misfolding of PAI-2, which may lead to impaired inhibitory activity. The misfolding may convert PAI-2 from an inhibitor of uPA to an activator of CAS. Misfolded PAI-2 may consequently contribute to the pro-inflammatory, pro-coagulant, and pro-fibrinolytic processes characterizing the development of PE (32).

### **Hypotheses**

[figure not shown]
- Alterations of CAS are involved in the pathophysiology of PE
- Misfolded PAI-2 impacts CAS
- Misfolded PAI-2 is present in plasma and placental tissue in women with PE

### **Aim of the study**

- To investigate the initiation, propagation, and inhibition of CAS in women with PE in comparison with a matching group of pregnant women without PE.
- To investigate the impact of misfolded PAI-2 on CAS.
- To develop immunochemical assays for determination of native and misfolded PAI-2 in human plasma and placental tissue.
- To assess the plasma concentration of native and misfolded PAI-2 in women with PE and matching controls

The procedures used for isolation of PAI-2 and development of immunochemical assays are illustrated in fig. 1.

### Development of plasminogen activator inhibitor 2 (PAI-2) assays and purification of PAI-2

**Fig. 1. Procedure for isolation of purified PAI-2 and development of PAI-2 assays**

### Patients and methods

Women ( $n = 113$ ) are included if they fulfil the diagnostic criteria for PE as given in the guideline from Danish Society of Obstetrics and Gynaecology (ref). For each woman with PE, a healthy woman is included ( $n = 113$ ). The control subject must be comparable ( $\pm 1$ ) with the case with respect to gestational week, age, parity, and body mass index. Patients will be included at Department of Obstetrics and Gynaecology, University Hospital of Southern Denmark, Esbjerg (SVS), and at Department of Obstetrics and Gynaecology, Odense University Hospital (OUH). Approximately 5,400 babies are delivered at the two hospitals annually.

The power calculation is based on the total amount of KK that can be generated in plasma after contact activation (16). The mean amount of KK determined in a reference population ( $n=85$ ) is 2172 mIU/ml x min with a standard deviation of 515 mIU/ml x min. The clinically relevant change in KK generation is estimated to 10%. With an alpha-value of 0.05 and a beta-value of 80% it can be calculated that  $2 \times 90$  women must be included in the study. The maximal dropout frequency is stipulated to 25% and consequently  $2 \times 113$

women must be included in the study. It should be noticed that the amount of KK that can be generated in plasma from pregnant women has not been determined so far.

Blood samples are collected from the patients at inclusion. Plasma samples are collected after centrifugation and frozen at - 80°C until analyses. Biochemical analyses are performed when all patients are included in the study. The Unit for Thrombosis Research has developed and possesses a number of methods for determination of the concentration and activity of the CAS proteins. Methods are available for determination of FXII (33), PK, F-a2M (15), C1-inh (34), KK-generation (16), C1-inh-FXIIa, C1-inh-KK, a2M-KK, and a2m-thrombin (under preparation). In relation to the project immunochemical and histochemical methods for determination of native PAI-2 and misfolded PAI-2 must be developed.

Placentas from the first 15 patients with PE and the first 15 control subjects are used for histochemical analyses and protein extraction.

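### The 25% dropout allowance is added to 90 rather than taken off the number enrolled: 113 per group leaves 84–85, not 90, and about 78% power

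*Protocol*

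**What the plan says.** The Patients and methods section of the protocol bases the sample size on total kallikrein (KK) generation. The reference-population mean (n = 85) "is 2172 mIU/ml x min with a standard deviation of 515 mIU/ml x min", and the relevant change is put at 10%. The calculation then reads "With an alpha-value of 0.05 and a beta-value of 80% it can be calculated that" 2 x 90 women are needed. The next step is the dropout allowance: "The maximal dropout frequency is stipulated to 25% and consequently" 2 x 113 women must be included. The figure of 113 also stands at the start of the section as the number of cases and the number of controls, with one matched control per case. The protocol gives no other dropout rate and no other inflation.

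**The concern.** The calculation presents 113 as what follows from needing 90 and losing up to 25%. It does not follow. A dropout frequency is a proportion of those enrolled, so the enrolment figure has to be divided by the retained fraction. Adding 25% to the evaluable number gives too few. As written, 2 x 113 enrolled, dropout up to 25% and 80% power cannot all hold. This is the protocol's only power calculation, so its one powered comparison falls short of its stated power at the loss the sponsor says it has allowed for.

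The calculation also labels 80% as beta. Beta is the type II error probability, so read literally the study would have 20% power. The intended meaning is clear from the result, but the statement is wrong as it stands.

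**Working it through.** **Inputs, all from Patients and methods:** mean 2172 and SD 515 mIU/ml x min; relevant change 10%, i.e. 217.2; alpha 0.05; 80%; 1:1 allocation; 25% maximum dropout. The protocol does not state sidedness or the test. I take a two-sided, unpaired comparison because that reproduces the stated 90; a one-sided test needs only 70 per group.

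**1. Reproduce the 90.** Standardised difference = 217.2 / 515 = 0.422.

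- Normal approximation: n = 2 x ((1.960 + 0.842) x 515 / 217.2)² = 88.3, so 89 per group.
- t test: 89.2, so 90 per group. The protocol's figure reproduces.

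**2. Check the beta label.** With power 80% (beta 20%) the result is 90, as above. With beta 80% (power 20%), the normal formula gives about 14 per group and the t test about 15. Only the first reading fits.

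**3. Reproduce the 113.** 90 x (1 + 0.25) = 112.5, rounded up to 113. This is the protocol's route.

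**4. The inflation that keeps 90.** 90 / (1 − 0.25) = 120 per group, 7 more per group and 14 more in total. Rounding does not explain the gap: the unrounded requirements give 88.25 / 0.75 = 117.7 and 89.2 / 0.75 = 118.9.

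**5. What 113 leaves.** 113 x 0.75 = 84.75, so 84 or 85 per group, 5 to 6 short of 90. The largest loss that still leaves 90 is 1 − 90/113 = 20.4%.

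**6. Power for a difference of 217.2 with SD 515, two-sided 0.05:**

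| Evaluable per group | t test | Normal approximation |
|---|---|---|
| 84 | 77.6% | 78.0% |
| 85 | 78.0% | 78.5% |
| 90 | 80.3% | 80.8% |
| 113 (no loss) | 88.4% | 88.7% |

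At 85 per group, the difference detectable with 80% power (t test) is about 10.25% of the reference mean instead of 10%.

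**The case against.** The arithmetic is not in dispute; the case on the other side is that it matters little.

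- **25% is a ceiling.** Power is at least 80% for any loss up to 20.4%, and 88.4% with no loss. That is right, and the shortfall should be described as conditional. But a sample size justified by a stated maximum loss should hold at that maximum.
- **Such a loss looks unlikely for this endpoint.** Blood is drawn when a woman enters the study and KK generation is measured in the stored plasma, so ordinary loss to follow-up cannot remove the value. Unusable samples, withdrawn consent or broken matches could. This is a fair reason to think actual losses will be below 25%, but the protocol neither defines dropout nor states a lower rate.
- **The SD is a larger uncertainty.** It comes from 85 reference subjects, and the protocol says KK generation has not been measured in pregnancy. If values are roughly normal (an assumption), the 95% interval for the SD is about 448–607, and power at 85 per group runs from about 88% down to 64%. This puts two points in proportion; it does not make 113 follow from 90 and 25%.
- **Matching might restore power.** In a paired analysis with an assumed within-pair correlation of 0.1, 84 complete pairs give about 81%. But if losses strike members of pairs independently, about 113 x 0.75² = 64 pairs remain, with about 70% power at that correlation. The protocol gives no correlation, so neither effect can be counted.
- **The beta label changes no number.** True; it is a wording correction and adds no weight to the dropout point.

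What stands is that the consequence is small and arises only above 20.4% loss. None of these points makes the stated figures agree.

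**Conclusion.** The concern holds. The step from 90 to 113 is wrong as written: 120 per group would be needed to keep 90 after a 25% loss. At that loss, the planned 113 leave 84–85 women per group and 77.6–78.0% power by t test (78.0–78.5% by normal approximation), so the study misses its stated 80% by about two points. Up to 20.4% dropout it does not miss. These power figures rest on a two-sided, unpaired comparison with the protocol's own mean, SD and 10% difference. The inconsistency between 90, 25% and 113 does not depend on the choice of test. The shortfall is modest and gives no reason to redesign the study, but the sample-size statement should be corrected. The beta-value is a separate mislabelling in the same calculation.

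**What to change.** Keep 2 x 113 and correct the power calculation in Patients and methods in one of two ways:

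- state that 2 x 113 preserves 80% power for dropout up to 20%; or
- keep the 25% maximum and state that about 85 per group would then remain, with power of about 78% (detectable difference at 80% power about 10.25%).

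In either case, replace the beta-value of 80% with a power of 80% (beta 20%), and name the two-sided unpaired comparison on which the figure rests.

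The cost is a sentence or two and a slightly less favourable stated figure; no extra women are needed. If the sponsor prefers to keep both 25% dropout and 80% power, the enrolment target becomes 2 x 120, which is 14 more women in total, and the two counts of 113 at the start of the section change with it.

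### Does taking placentas from the first 15 cases and first 15 controls, with no matching on week of delivery, undermine the placental PAI-2 work?

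*Protocol*

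**What the plan says.** Under Patients and methods the protocol sets the tissue sample: "Placentas from the first 15 patients with PE and the first 15 control subjects are used for histochemical analyses and protein extraction". It gives no rationale for the number 15 and does not require the 15 controls to be the partners of the 15 cases. One healthy control is recruited per case and must be comparable, within 1, "with the case with respect to gestational week, age, parity, and body mass index". The time point of the gestational week is not written out. Since "Blood samples are collected from the patients at inclusion", inclusion is the natural reading. Week at delivery is not a matching variable.

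Three other statements bear on the point:

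- Background: "PE is a major risk factor for iatrogenic induced prematurity".
- Section on PE and PAI-2: "The plasma concentration of PAI-2 increases to high levels through pregnancy". This is a statement about plasma, not tissue.
- Hypotheses and Aim of the study: the hypothesis involving placental tissue reads "Misfolded PAI-2 is present in plasma and placental tissue in women with PE", and the case-control aim for PAI-2 reads "To assess the plasma concentration of native and misfolded PAI-2 in women with PE and matching controls". A separate aim is to develop assays for native and misfolded PAI-2 in plasma and placental tissue.

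**The concern.** A control matched to her case at inclusion may carry on to term while the case is delivered early. The matching that protects the plasma comparison therefore does not protect a comparison of placentas. If PAI-2 in placental tissue changes with gestational age, as it does in plasma, a difference between the two sets of 15 could not be attributed to PE rather than to placental age. Counting the first 15 of each group separately may also break up matched pairs. The choice of tissue is fixed in the protocol, so a later analysis plan could repair it only in part. Collecting control placentas in equal number makes a side-by-side reading easy to foresee.

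**Working it through.** **The plan's own figures.** The 15 + 15 placentas come with no calculation to reproduce. The protocol's sample size is for kallikrein generation in plasma: n per group = 2 × (1.960 + 0.842)² × 515² / 217.2² ≈ 88.3, so 89; the t-test version gives 89.2, so the stated 90. It has no bearing on the placentas.

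**What each stated purpose needs from the placentas.**

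| Stated purpose | Uses placentas? | Needs equal week at delivery? |
|---|---|---|
| Misfolded PAI-2 is present in PE plasma and placenta (Hypotheses) | Yes, PE tissue | No, it is a claim of presence |
| Assays for native and misfolded PAI-2 in plasma and placenta (Aim of the study) | Yes, as material | No |
| PAI-2 in PE against matched controls (Aim of the study) | No, plasma only | No, blood is drawn at inclusion |

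No row requires a contrast of PE and control placentas.

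**If a contrast were made anyway.** With 15 against 15, an unpaired two-sided t test at 0.05 has 80% power for 1.06 SD. Suppose placental age alone shifts the mean by an assumed amount and PE has no effect. The chance of declaring a difference is then:

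| Assumed shift due to age (SD) | Chance of a significant result |
|---|---|
| 0 | 5% |
| 0.25 | 10% |
| 0.5 | 26% |
| 0.75 | 51% |
| 1.0 | 75% |

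The documents give no distribution of week at delivery and nothing on tissue PAI-2 by week, so they do not say which row applies.

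**What counting the groups separately costs.** Assume each control is enrolled after her case with an exponential delay, measured in intervals between successive cases. By simulation, mean delays of 0, 2, 5, 10 and 20 intervals leave on average 15.0, 14.3, 13.2, 11.9 and 10.2 of the first 15 controls partnered with one of the first 15 cases. Unless controls are slow to find, most pairs survive.

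**What loss of placentas might cost.** On dropout the protocol says "The maximal dropout frequency is stipulated to 25" per cent, as a maximum for the main study. If that applied to placentas, independently within a pair, and the rule meant 15 women enrolled rather than 15 placentas obtained, complete pairs would number 15 × 0.75² = 8.4. The protocol states none of these three conditions.

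**Would complete pairs help?** Pairs are matched on week at inclusion, so both members can be present and still deliver weeks apart. The age difference between the sets remains.

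**Would adjustment be hopeless?** For two equal groups with a gap d in mean week of delivery and within-group SD s, adjusting for week multiplies the residual variance by 1 + d²/(4s²). For s = 3, d = 2 this is 1 + 4/36 = 1.11; for s = 2, d = 6 it is 1 + 36/16 = 3.25. Read as the net loss, these give detectable differences of 1.06 × √1.11 = 1.12 SD and 1.06 × √3.25 = 1.91 SD. That reading assumes week explains none of the outcome within groups, in which case there would be no confounding by week to remove. With an assumed within-group correlation of 0.5, the residual variance is 1 − 0.25 = 0.75 of the total. The net factors become 0.75 × 1.11 = 0.83 and 0.75 × 3.25 = 2.44, and the detectable differences about 0.97 and 1.65 SD. At the mild end adjustment gains precision.

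**The case for a change.** The best case for a change is that 15 control placentas serve little purpose unless someone compares them with the 15 from PE, that the sampling rule is fixed here, and that the remedy is cheap: the same 30 placentas, one extra date per woman, and at 25% loss about 15 / 0.5625 ≈ 27 of the 113 pairs approached.

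Part of this stands. A contrast is foreseeable, the match does not cover week at delivery, and an unadjusted difference should not be read as an effect of PE. The rest does not carry a change. Control tissue can also serve as reference material for assays and extraction. Figure 1, which deals with PAI-2 isolation and assay development, cannot be seen in the text at hand, so it may show such a role. The pair rule would not address the age difference. What would help is to have the week of delivery to hand, show results against it, and call a contrast descriptive; an analysis plan commonly holds that. The protocol lists no clinical variables to be recorded, so its silence on delivery date does not show that the date will be missing.

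**Conclusion.** No change to the protocol is needed. The observation is correct as a caution: matching at inclusion does not equalise gestational age at delivery, so a contrast of the two placenta sets could be confounded by placental age, in a direction and to an extent that the documents do not reveal. If most cases are included near term, the effect is small. No stated hypothesis or aim depends on that contrast, and the planned plasma comparison is untouched. Following the plan as written therefore leaves its stated conclusions sound. Complete pairs would add little, since they leave the age difference in place. An analyst who does compare the placentas can handle the point by showing PAI-2 against week at delivery and reporting the comparison as descriptive. This conclusion assumes that the matched week is the week at inclusion and that the placentas serve the purposes the protocol states. If a placental case-control endpoint were added, the question would need to be reopened.
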